9.3 POPULATIONS FOR ANALYSES

Analyses will be intention-to-treat (ITT); patients will be analyzed according to their randomized group, regardless of adherence to treatment.

9.4 STATISTICAL ANALYSES

9.4.1 GENERAL APPROACH

Model fits will be examined using residual versus fitted value plots, and we will examine jackknife influence plots to assess potential high leverage observations. If such observations have an undue influence on the final result (in either direction), this will be reported. Inadequate model fit will be addressed using transformations, as well as higher order terms in the regression if needed. The number of such exploratory models will be reported. Such fits will be reported. Robust (Huber) regression may be reported as a methodological sensitivity analysis.

DETECT

Version 5.0
21 March 2023

9.4.2 ANALYSIS OF THE PRIMARY EFFICACY ENDPOINT

DETECT I

1. UT-DSA EK versus DMEK: The primary analysis will be 12-month BSCVA. We will use a mixed effects linear regression model to evaluate BSCVA measured at 12 months with fixed effects for surgical treatment arm (expressed as a binary indicator variable for UT-DSA EK versus DMEK), drug treatment arm (expressed as a binary indicator variable for Ripasudil versus Placebo) and baseline BSCVA. We will include random effects for clinic site and patient.
2. Adjuvant Ripasudil versus Placebo: The primary analysis will be 12-month ECL. We will use a mixed effects linear regression model to assess 12-month ECD with fixed effects for treatment arm (expressed as a binary indicator variable for Adjuvant Ripasudil versus placebo), surgery (expressed as a binary variable for UT-DSA EK versus DMEK), baseline ECD (as measured by the eye bank). We will include random effects for clinic site and patient.

We have no reason to expect that ripasudil would work better with one surgery versus another. A secondary analysis of the primary outcomes will also include a fixed effect interaction term for Drug x Surgery. This will enable us to estimate the effect of UT-DSA EK versus DMEK on BSCVA with- and without the adjuvant ripasudil, and to estimate the effect of Ripasudil on ECL separately by type of surgery. If there is a statistically significant interaction between treatments with respect to either outcome we will report stratified results, though we concede that the trial will have low power to detect an interaction unless the interaction effect is twice as large as the detectable effect sizes reported above in **Section 9.2**.

DETECT II

1. DMEK versus DSO: The primary analysis will be 12-month BSCVA. We will use a mixed effects linear regression model to evaluate BSCVA measured at 12 months with fixed effects for treatment arm (expressed as a binary indicator variable for DMEK versus DSO) and baseline BSCVA. We will include random effects for clinic site and patient.

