6.3 MEASURES TO MINIMIZE BIAS: RANDOMIZATION AND BLINDING

For both trials, patients will be randomized by the eye bank 1-3 weeks prior to surgery. In DETECT I, each study eye will be randomly assigned separately to the two treatment groups (DMEK/UT-DSAEK, ripasudil/placebo). Block randomization will be performed using a computer program (Statistical package R; Version 3.6; R Foundation for Statistical Computing, Vienna Austria) by the data coordinating center. Once an eye is enrolled in the study, the study coordinator will assign the study participant's eye an ID (alpha-numeric code).

Prior to surgery, the eye bank will assign the study participant corneal tissue. Once the corneal tissue has been assigned, the eye bank will look at the treatment assignment with regard to surgical treatment and prepare the tissue accordingly. For DETECT II, the tissue will be randomized and assigned to the patient if the patient is randomized to DMEK. The eye bank will also inform the surgeon of the study participant's randomization assignment with regard to type of surgery.

The eye bank will randomize tissue using the Microsoft Excel RANDBETWEEN formula. A new file will be created for each study eye and uploaded to REDCap. The eye bank will highlight the randomized tissue in the Excel file (the randomization runs every time the file is opened), so the original randomization is documented. If tissue does not pass post-processing evaluation, becomes ineligible for some other reason, or it does not meet study parameters, e.g. >90 microns, the randomization process will be repeated, the same Excel file can be used.

Once the study eye has been assigned a study participant ID and randomized to treatment group they will be included in the intention to treat analysis. (Note: See **MOP – Section 4.3** for full donor tissue procurement and assignment information).

All study participants will be masked to their intervention. The refractionist performing the BSCVA will also be masked. Due to the nature of the intervention, the surgeon and technician performing study visit endothelial cell counts and

DETECT

Version 5.0
21 March 2023

other imaging will not be masked as to surgery type (but will be masked as to study medication); however, image graders at the Proctor Reading Center and CIARC will be masked. Eye bank personnel will not be given any identifying information.

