9.2 SAMPLE SIZE DETERMINATION

DETECT I

We will power the study for each comparison. For both primary analyses, we used a standard sample size formula based on an ANCOVA that conditions on a baseline outcome measure.⁴⁹ Given that endothelial cell density and visual acuity are different, non-correlated outcomes ($R=0.08$ in the DETECT pilot study) with different randomization, each will have its own alpha of 0.05. Specifically, we will be comparing:

- I. With 80 patients per group (160 total), we estimate that we will have at least 90% power to detect a difference in logMAR of 0.11 at 12 months, assuming an outcome SD of 0.2, a 2-sided alpha of 0.05, and 10% loss-to-follow-up. Under the same assumptions but 80% power, the minimum detectable difference in logMAR is 0.09. We assumed a higher SD in the calculation compared with the SD estimated in the DETECT pilot (adj. SD=0.147) to allow for more complex eyes enrolled in the trial.
- II. With 80 patients per group (160 total), we estimate that we will have at least 90% power to detect a 7% difference in ECL between enrollment and 12 months, assuming an outcome SD of 0.134 estimated from the DETECT pilot study, a 2-sided alpha of 0.05, and 10% loss-to-follow-up. If we assume a larger outcome SD for more complex eyes (SD=0.18), we will have at least 90% power to detect a 10% difference in ECL.

DETECT II

With 30 patients per group (60 total), we estimate that we will have at least 90% power to detect a difference in logMAR of 0.13, assuming an outcome SD of 0.147, a 2-sided alpha of 0.05, and 10% loss-to-follow-up. The SD was estimated from the DETECT pilot study and was adjusted for correlation between baseline and 12-month measurements (outcome SD = 0.163, correlation = 0.428, adjusted SD = 0.147). Under the same assumptions but 80% power, the minimum detectable difference is 0.11 logMAR.

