CIARC is the leading centralized reading center for endothelial image analysis in the United States, in part based on its experience over the past nearly 20 years with the NEI-supported Specular Microscopy Ancillary Study (SMAS) and the Cornea Preservation Time Study (CPTS), leading to numerous publications and providing key insights into the donor, recipient, operative, and postoperative factors that influence ECL following PKP (SMAS) and DSAEK (CPTS). The CIARC will perform dual grading and adjudication, when required, of each image using established methods for determination of endothelial cell density and morphometric parameters. The CIARC will perform eye bank (2) and clinical site (5) training, external calibration for specular microscopes as well as eye bank and clinical site technician certification (minimum of 2 technicians per site). The CIARC will analyze 3 eye bank screening images of the central donor endothelium and 3 images of the grafted central endothelium postoperatively at 6, 12 and 24 months for the 220 study eyes for a total of 2,640 images.

[name] is the Charles I Thomas Professor and Vice Chair for Academic Affairs in the CWRU Department of Ophthalmology and Visual Sciences and has been the Medical Director of the Cornea Image Analysis Reading Center (CIARC) since 1988. He served as Medical Director for the CIARC for the NEI-funded Specular Microscopy Ancillary Study (SMAS) and the Study Chair as well as Medical Director for the CIARC in the NEI-funded Cornea Preservation Time Study (CPTS). For the DETECT, as Medical Director of the CIARC, he will have the following responsibilities similar to his activities for the CPTS: 1) participate in the scientific plan for the DETECT; 2) oversee administrative functions outlined in the CIARC Operations Manual; 3) will interface with clinical sites and eye banks when direct physician contact is mandated; 4) review Scientific Director (CIARC) prepared reports to the Clinical Coordinating Center, Data Coordinating Center, DSMC, and the NEI; 5) meet on a weekly basis with the Scientific Director (CIARC) to review conduct of the study; 6) participate on regular Steering Committee calls of the DETECT administrative team; and 7) participate in data analysis, manuscript preparation, and presentations in conjunction with the to the Clinical Coordinating Center, Data Coordinating Center, DSMC, and the NEI.

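### The primary cell-loss model takes baseline ECD from the eye bank, although the reading centre is already due to read donor images by the method used at 12 months

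*Protocol*

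**What the plan says.** For the second DETECT I primary analysis, Section 9.4.2 states: "We will use a mixed effects linear regression model to assess 12-month ECD with fixed effects for treatment arm", with surgery and "baseline ECD (as measured by the eye bank") as further fixed effects, and random effects for clinic site and patient.

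The description of CIARC under Section 10.1.5 gives the reading plan. "The CIARC will analyze 3 eye bank screening images of the central donor endothelium", and also "3 images of the grafted central endothelium postoperatively at 6, 12 and 24 months", "for the 220 study eyes for a total of 2,640 images". CIARC will "perform dual grading and adjudication, when required, of each image using established methods for determination of endothelial cell density". Section 6.3 adds that "image graders at the Proctor Reading Center and CIARC will be masked". The same description makes CIARC responsible for training the two eye banks, calibrating specular microscopes and certifying technicians.

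The starting point for endothelial cell loss (ECL) is worded differently elsewhere. Section 9.2 claims "at least 90% power to detect a 7% difference in ECL between enrollment and 12 months". Section 9.1 speaks of pre-operative ECD. Section 9.4.5 lists donor counts both before and after processing, and Section 9.4.2 does not say which one its covariate is.

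**The concern.** As written, the baseline covariate and the outcome come from different measurers, although a donor reading by the outcome's own reader is already planned. Two things are at stake. Random disagreement between readers makes the covariate less reliable, so adjustment removes less variance. A systematic difference moves any percent ECL calculated as 12-month CIARC density over an eye-bank count, and ECL is how the endpoint and the power statement are expressed.

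The definition is also loose. At enrollment the recipient still has the diseased endothelium, which the Schedule of Activities images at screening and Visit 1; that is not the graft's baseline. Section 6.3 has the eye bank prepare tissue according to the surgical assignment, so a post-processing count follows surgical randomisation. Adjusting for it would take any preparation loss out of the DMEK versus UT-DSAEK comparison of 12-month ECL, a key secondary outcome in Section 9.4.3.

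**Working it through.** **1. Are donor images in the reading plan?** Four occasions (donor, 6, 12, 24 months): 220 × 3 × 4 = 2,640, the stated total. Without donor images it would be 220 × 3 × 3 = 1,980. The total counts donor images even for the 30 DSO eyes, which receive no donor tissue; this does not touch DETECT I.

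**2. The plan's power figure.** Section 9.2: 80 per group, 10% loss, so n = 72; difference 0.07; SD 0.134; two-sided alpha 0.05.
- Standard error = 0.134 × √(2/72) = 0.02233.
- Power = Φ(0.07/0.02233 − 1.960) = Φ(1.174) = 88.0%.
- Difference detectable with 90% power = 3.2415 × 0.02233 = 0.0724, which rounds to the stated 7%.

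**3. Systematic offset.** If the eye bank reads a proportion c high in all arms, the covariate becomes (1+c) × baseline. Its coefficient shrinks by that factor and the treatment coefficient is unchanged. If percent ECL is calculated instead, 1 − ECL is divided by (1+c) in every eye, so the between-arm difference and its SD shrink together.

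The level does move. From the pilot means (post-processing donor count to 12 months: UT-DSAEK 2796 to 2070, DMEK 2771 to 1855), with c assumed:

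| c | ECL UT-DSAEK | ECL DMEK | Difference, points |
|---|---|---|---|
| −10% | 17.7% | 25.6% | 7.9 |
| 0 | 26.0% | 33.1% | 7.1 |
| +10% | 32.7% | 39.1% | 6.4 |

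**4. Random reader error, by formula.** The documents give neither an eye-bank versus CIARC disagreement nor an ECD baseline-to-12-month correlation; the 0.428 in Section 9.2 belongs to the logMAR calculation. Both are therefore assumed. Let 0.134 be the adjusted SD with a fully reliable baseline, ρ the correlation and λ the reliability of the eye-bank count. The residual SD is 0.134 × √[(1 − λρ²)/(1 − ρ²)]. For ρ = 0.3 and λ = 0.4 it is 0.134 × √(0.964/0.91) = 0.1379.

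| ρ | Power, λ = 1 | λ = 0.8 | λ = 0.4 |
|---|---|---|---|
| 0.1 | 88.0% | 87.9% | 87.8% |
| 0.3 | 88.0% | 87.4% | 86.1% |
| 0.5 | 88.0% | 85.9% | 81.6% |

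**5. Random error and offset together, by simulation.** Assumed: 72 eyes per drug arm, surgery balanced, donor ECD mean 2,780 and SD 200. Twelve-month ECD is baseline × (0.70 + 0.07 for ripasudil − 0.07 for one surgery) plus error of SD 0.134 × 2,780 = 372.5. Ordinary regression on drug, surgery and baseline, without random effects; 3,000 replicates. True drug effect: 0.07 × 2,780 = 194.6 cells/mm².

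| Baseline covariate | Mean drug effect | SE | Power |
|---|---|---|---|
| No offset, no error | 193.5 | 62.9 | 87.0% |
| +5%, error SD 100 | 194.6 | 63.3 | 85.9% |
| +10%, error SD 200 | 194.4 | 66.2 | 84.5% |

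Simulation error in each power is about √(0.87 × 0.13/3000) = 0.6 points, so the first drop is barely resolved. The implied spread of the eye-bank count is √(210² + 100²) = 233 in the second row and √(220² + 200²) = 297 in the third. The pilot SDs in Section 9.4.5 run from 150 to 238, so the third row is pessimistic.

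**6. Processing loss in the pilot (Section 9.4.5).** UT-DSAEK 2792 to 2796, +4; DMEK 2797 to 2771, −26 cells/mm². The arms differ by 30, about 1% of the count.

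**The case against.** The bracketed words may only separate donor ECD from recipient ECD, naming the place of measurement and not the grader. The manual of procedures, the CIARC appendix and the SAP, none of which is at hand, may already name the CIARC reading. CIARC trains the eye banks and calibrates microscopes, which works directly against reader offset. Baseline precedes the drug, so the ripasudil contrast is safe, and the pilot shows almost no preparation loss.

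Most of this stands, and it limits the size of the point. It does not settle the wording: the protocol names one measurer while planning a reading by another, and a sentence that can be read two ways in a primary model should be fixed.

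Three stronger readings are tempting, and the documents do not support them:
- **That the eye bank and CIARC count the same images.** CIARC reads eye-bank screening images; nothing says which images the eye bank counts from, or that the screening images precede processing.
- **That the shift in ECL level can be set against the 7% target.** The shift occurs in both arms; the target is a difference between arms.
- **That precision loss is large.** Assuming 10% reader error means about 279 cells on a count of 2,790, more than the whole pre-processing SD of 210–222 in the pilot. If those are eye-bank counts, which is not stated, that is impossible. If the pilot SD of 0.134 already rests on eye-bank baselines, also not stated, the loss is already in the planned power and a CIARC baseline would be a gain.

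**Conclusion.** The point holds as a modest one about consistency and precision. Section 9.4.2 names the eye bank's measurement although a masked, dual-graded donor reading by the outcome's own method is planned, and Section 9.2 starts ECL from a different place. The randomised ripasudil effect is not biased by a reader difference common to the arms. The precision cost is small: roughly 87% to 84–86% power in the simulation, nearer the upper figure if reader error fits the pilot's spread. The formula falls further, to 81.6%, only if correlation is strong and more than half of the variance in the eye-bank count is error. All of this rests on assumed reader error and correlation. The reported level of percent ECL can move, by an amount the documents do not give. The processing question concerns only the surgery comparison and looks minor on pilot figures.

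**What to change.** - In Section 9.4.2, name the CIARC reading of the donor screening images as baseline ECD, and define ECL from the same reading.
- Use the eye-bank count where donor images are unreadable, and repeat the analysis with it throughout as a sensitivity analysis.
- State whether the screening images are taken before tissue processing. If a pre-processing reading is available, use it for the DMEK versus UT-DSAEK comparison of ECL.
- In Section 9.2, replace the reference to enrollment with this donor baseline.

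The cost is a few words in the protocol, matched in the SAP. The readings are already planned and the change alters no stated figure. The drawback is that some donor images may prove unreadable, so the fallback rule must be written down beforehand. If the sponsor prefers the eye-bank count, a sentence of justification saying which count is meant would also close the gap.

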4.2 SCIENTIFIC RATIONALE FOR STUDY DESIGN

Randomized control trials are known to be the least biased form of evidence. The factorial design of this trial is efficient, allowing us to perform two randomized trials simultaneously. It is very unlikely that there will be an interaction between surgery and ripasudil. All patients will receive standard of care treatment.

DETECT

Version 5.0
21 March 2023

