Benefits. An unmasked interim analysis will be conducted to determine whether or not sufficient evidence has accumulated to justify stopping one or both factorial treatments. The guidelines for efficacy will use group sequential boundaries for judging the statistical significance of the primary outcome measure. The trial will use the Lan and DeMets flexible alpha spending approach with a power function, with $\alpha^*(t^*) = \alpha (t^*)^\theta$, where $\alpha = 3.561$ (chosen so that the two-sided P -value to stop the trial for efficacy is 0.001).⁵⁴ We propose a single interim analysis at the midpoint of the trial, i.e. when full outcome data are available for one half of the subjects. If one surgery method is clearly superior with respect to BSCVA, with no evidence for interaction with the ripasudil, then future patients will receive the better surgery method and still be randomized to ripasudil vs placebo. If ripasudil is clearly superior to placebo with respect to ECD, with no evidence for interaction by type of surgery, then future patients will receive ripasudil and would still be randomized to surgery type. At the interim analysis, tests for interaction will have very low power and so any decision to stop a single treatment early for benefit would be done in consultation with the DSMC.

Harm. Stopping one or both treatments for harm will be done at the judgment of the DSMC. Several endpoints will be examined, including (a) the best spectacle-corrected visual acuity at 12 months (b) adverse events, and especially (c) serious adverse events, including primary graft failure or mortality. While the analysis would consider maldistribution of predictive factors such as (a) age (b) visual acuity at presentation, and (c) diagnosis of PACE, it is recognized that ethical considerations require careful considerations of statistical tests as well as qualitative judgments in the light of experience.

Futility. Early discontinuation due to the unlikelihood of significant findings for both primary analyses conditional on interim results may be considered pending discussion with the DSMC.

DETECT

Version 5.0
21 March 2023

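### DETECT I promises stratum-specific results only after a significant Drug x Surgery test, which would miss an interaction as large as the design effect about 62 to 65% of the time

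*Protocol*

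**What the plan says.** Section 9.4.2 fixes the two DETECT I primary analyses as main-effects models: BSCVA at 12 months for surgery, and 12-month endothelial cell loss for ripasudil. Each is adjusted for the other factor, and neither has an interaction term. A secondary analysis of both outcomes adds Drug x Surgery. Its stated purpose is to estimate the surgery effect with and without ripasudil, and the ripasudil effect separately by surgery. The reporting rule follows: "If there is a statistically significant interaction between treatments with respect to either outcome we will report stratified results". The same sentence concedes low power unless the interaction is twice the detectable effect. Nothing is said about what is reported when the test is not significant.

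Section 4.2 gives the design assumption: "It is very unlikely that there will be an interaction between surgery and ripasudil". Section 9.4.6 uses similar reasoning for stopping one factor early. The condition for surgery begins "If one surgery method is clearly superior with respect to BSCVA, with no evidence for interaction with the ripasudil", and a parallel one covers ripasudil. That section adds that interaction tests will have very low power at that point, and that such a decision would be made in consultation with the DSMC.

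**The concern.** The trial will hold the within-stratum estimates anyway, because the secondary model is built to produce them. Tying their reporting to a test the protocol itself calls weak has two consequences. First, when the effects do differ, the usual committed output is one averaged effect per factor, and the reader cannot see how far apart the strata were. Second, stratum estimates that appear only after a significant test are a selected set, chosen because they happened to lie far apart, so they tend to exaggerate the difference.

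The question is not idle here. The protocol hypothesises higher cell loss after DMEK than after UT-DSAEK, and section 2.2 presents rho-kinase inhibition as a possible answer to cell loss after DMEK. Readers will want the ripasudil effect within DMEK, and the plan commits to showing it only conditionally.

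**Working it through.** **Inputs, all from section 9.2.** There are 80 patients per margin and 10% loss, so 72 evaluable per margin. Equal allocation to the four cells (an assumption) gives 36 per cell. The BSCVA claim is "at least 90% power to detect a difference in logMAR of 0.11 at 12 months"; the SD behind it is 0.2 and the test is two-sided at 5%. The ECL claim is "at least 90% power to detect a 7% difference in ECL between enrollment and 12 months" with SD 0.134; the alternative for more complex eyes is 10 points with SD 0.18. On alpha, "each will have its own alpha of 0.05". Section 9.4.2 gives no level for the interaction test, so two-sided 5% is assumed. The stated SDs are used as residual SDs.

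**Formulas.**
- Main effect: SE = SD x sqrt(2/72) = SD/6.
- Interaction (difference of two differences over four cells): SE = SD x sqrt(4/36) = SD/3, twice the main-effect SE.
- Power = Phi(delta/SE - 1.96).

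**The protocol's own figures first, then an interaction of the same size.**

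| Case | Main SE | Main power | Interaction SE | delta/SE | Interaction power | Missed | 95% CI half-width |
|---|---|---|---|---|---|---|---|
| BSCVA 0.11, SD 0.2 | 0.0333 | 91.0% | 0.0667 | 1.65 | 37.8% | 62.2% | 0.131 |
| ECL 0.07, SD 0.134 | 0.0223 | 88.0% | 0.0447 | 1.57 | 34.7% | 65.3% | 0.0875 |
| ECL 0.10, SD 0.18 | 0.0300 | 91.5% | 0.0600 | 1.67 | 38.5% | 61.5% | 0.118 |

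The main-effect powers reproduce section 9.2. For ECL at SD 0.134 the difference detectable with 90% power is 7.24 points, which rounds to the stated 7. Doubling the interaction restores the main-effect powers (91.0%, 88.0%, 91.5%), so the protocol's remark about an interaction twice as large is correct.

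**Sensitivity.** With no dropout (40 per cell) the miss rates are 58.7%, 62.1% and 58.1%. At the pilot's adjusted BSCVA SD of 0.147, which section 9.2 sets aside for DETECT I in favour of 0.2, the SE is 0.147/3 = 0.049, delta/SE is 2.24 and about 39% are missed.

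**What a non-significant test leaves open.** The interval then contains zero and is 2 x 0.131 = 0.26 logMAR long, so at least one end lies 0.13 or more from zero. An interaction of 0.11 in at least one direction therefore always remains compatible with the data. The same holds for ECL: 8.8 points against 7, and 11.8 against 10.

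**What a significant test selects.** Significance needs an observed interaction above 0.131 logMAR, 8.8 points or 11.8 points respectively. If the true interaction equals the design effect, every significant result in the right direction overstates it.

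**Full effect with one surgery, none with the other.** The interaction equals the design effect and the main effect is half of it. For BSCVA, 0.055/0.0333 = 1.65, so main-effect power is also about 38% (35% for ECL at SD 0.134). The within-stratum contrast, 36 against 36, has SE = SD x sqrt(2/36): 0.0471 for BSCVA and 0.0316 for ECL. Its power for the full effect is about 65% and 60%. Reporting of the more sensitive contrast thus hangs on the less sensitive test.

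**Half-way look.** With 36 per margin (18 per cell), SE = SD x sqrt(4/18): 0.0943 for BSCVA and 0.0632 for ECL. Power is 21.4% and 19.7%, so about 79% and 80% are missed.

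**The case against.** Main-effects primary analyses with a prespecified secondary interaction test are the conventional form of a factorial trial, and the protocol discloses the test's low power in both 9.4.2 and 9.4.6. The miss rate puts a number on a limitation already admitted. The interaction model is planned in order to estimate the separate effects, and nothing says they will be suppressed. Section 9.4.3 shows that a SAP exists, and it may promise fuller tables. All of this stands, and it makes the point one of reporting only. It does not remove it: admitting low power is a reason not to condition on the test, and the protocol's one stated rule does so.

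Several stronger readings are tempting but unsupported:

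- A reader might infer that the plan treats a null test as proof of no interaction. It never says so, does not write that stratified results appear solely on significance, and its concession of low power points the other way.
- A reader might infer that a false-positive interaction would displace the main result. The interaction model is secondary, and stratified results are not said to replace the primary analysis.
- A reader might pair SD 0.18 with a 7-point difference and obtain a worse miss rate. Section 9.2 pairs that SD with 10 points.
- A reader might infer that a benefit confined to one surgery would be claimed for both. In that scenario the halved main effect has only about 35 to 38% power, so a significant pooled benefit is not the likely outcome.
- A reader might take the interim condition as an automatic gate. It also requires clear superiority against a two-sided P of 0.001, and the decision goes through DSMC consultation.

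**Conclusion.** The point holds as a reporting defect. The protocol's only commitment to stratified results depends on a test that would miss an interaction equal to the design effect about 62% of the time for BSCVA, 65% for ECL at SD 0.134 and 61.5% for ECL at SD 0.18. This rests on equal cell sizes, 10% loss, two-sided 5% and the protocol's SDs taken as residual SDs. A non-significant result cannot exclude an interaction of design size, and conditioning on significance makes the published stratum estimates selective. The primary main-effects analyses, their alpha and the sample size are not in question. This is a cheap improvement to make before unmasking.

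**What to change.** In 9.4.2, replace the conditional sentence with text such as:

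> For both DETECT I primary outcomes we will report, whatever the interaction p-value, the main effect (which remains primary), the interaction estimate with its 95% CI, and the surgery effect within each drug arm and the ripasudil effect within each surgery, each with a 95% CI. A non-significant interaction will not be described as absence of interaction.

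Keep the existing statement about low power. In 9.4.6, state that the DSMC, already consulted on stopping a single factor, will be shown the same interaction and stratum-specific estimates with confidence intervals. Align the SAP.

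The cost is one sentence in 9.4.2, one edit in 9.4.6 and one extra table. No data or models are added. The downside is that the stratum intervals will be wide: about 0.092 logMAR either side for BSCVA (1.96 x 0.0471) and 6.2 points for ECL at SD 0.134 (1.96 x 0.0316). They should be presented as estimates, not as further confirmatory tests.
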